4. ADVERSE EVENT MANAGEMENT AND REPORTING

A record of all adverse events relating to subjected device (see Risk Analysis Section) and operative procedure, including details of the nature, onset, duration, severity, will be made on the

relevant section(s) of the subject's CRF. The subject will be questioned about any adverse event(s) at each subsequent follow-up assessment visit.

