2.3. PRIMARY AND SECONDARY ENDPOINTS

PHASE 1: Immediate post-op to 3 years	
Primary endpoints	Early bedding in
Secondary endpoints	At all follow-up visits: Survivorship up to 3 years JOA Radiographic Assessment Complications including revisions
PHASE 2: 5 to 10 years	
Primary endpoints	Steady-state wear
Secondary endpoints	At all follow-up visits: Survivorship up to 10 years JOA Radiographic Assessment Complications including revisions

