2.4. ASSESSMENT PROCEDURE

2.4.1. ASSESSMENT PARAMETERS AND METHODS

Medical History and Demographic Data

Demographic information will be collected, a detailed medical history will be obtained and a physical examination will be performed (including height, weight).

Clinical Assessments

An operative record will be completed to record details of each operative procedure and of the used implants.

Data to determine the clinical and functional performance of the device will be collected. Pre-operative and post-operative analysis will be compared using recognized and validated systems (JOA Score).

Radiographic Assessments (including Radiographic Assessment protocol)

A radiographic assessments including polyethylene wear analysis and cup inclination angle will be completed at each follow-up period.

The X-rays must be taken according to the Martell technique*, which requires an A/P pelvis view centered over the pubis. See attachment for radiographic technique.

For the polyethylene wear analysis, all Radiographic images will be determined and the penetration rate will be measured by Hip Analysis Suite (software program, [name] at Chicago University).

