2.4.2. ASSESSMENT TIMELINES/SCHEDULE

Example of Tabulated Assessment Schedule

	PRE-OP	SURGERY	PHASE 1						PHASE 2		
			IMMEDIATE POST-OP	6 WK	6 MO	1 YR	2 YR	3 YR	5 YR	7 YR	10 YR
Informed Consent	X										
Demographic and Historical Record	X										
Operative Record		X									
Radiographic Assessment			X	(X*)	X	X	X	X	X	X	X
JOA	X				X	X	X	X	X	X	X
Complications including Revisions			ANYTIME								

* Baseline for bedding in and total penetration rate

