6.2. CASE REPORT FORMS

Data for this clinical trial will be collected and documented on the subject Case Report Forms (CRFs) provided, which may be in paper form or in an electronic form. Authorized study site personnel will complete CRFs only. CRFs must be reviewed and signed by the Investigator or his/her designees.

Since there is a potential for errors, inaccuracies, and misinterpretation in transcribing data onto the CRFs, the following documents must be available at all times for inspection and comparison to the CRFs by the study monitor where appropriate:

- data query forms
- originals and photocopies/certified copies of all relevant records and reports
- copies of test results

Sample CRFs to be used with this clinical trial are provided in Appendix 2.

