8. RISK ANALYSIS

This clinical study is to collect data on the E1 liner and Delta Ceramic and CoCr femoral head hip system which is intended to help the participant gain mobility and decrease pain. Risks associated with this Hip system include general surgical and Hip arthroplasty risks. Due to the investigational nature of the system, there are unknown risks.

General Surgical Risks

As with any surgical procedure, there are risks involved with total joint replacement surgery. Potential adverse events include, but are not limited to: early or late infection perhaps necessitating device removal; component dislocation; damage to nerves and blood vessels; fracture of the bone or device; device loosening; allergic reactions to the metallic devices; phlebitis; long-term swelling; pulmonary embolization; and delayed wound healing. Other potential adverse effects include: prolonged illness; hematoma; wound dehiscence and/or drainage; the need for blood transfusions and/or further surgery; or permanent pain; deformity; and inconvenience. Risks associated with the anesthetic are those such as permanent brain damage, pneumonia, blood clots, and heart attack. Rarely some adverse events may be

fatal. These possible adverse events are not unique to the 1 liner and Delta Ceramic and CoCr femoral head hip system and, as stated above, may occur with any total joint replacement surgery.

As with any joint replacement post-operative activity, limitations may be imposed depending upon the participant's age, general health, baseline (pre-operative) activity level and baseline (pre-operative) condition of the Hip and other joints.

Potential Risks Associated with E1 liner and Delta Ceramic and CoCr femoral head hip system

As with all hip replacement systems, potential adverse effects include risk of infection, loosening of the components, breakage or bending of the components, or change in position of the components any of which can necessitate removal and/or revision surgery. There have been reports of sensitivity reactions to the components of Hip systems. Other potential adverse effects of Hip replacement surgery include neurovascular damage, dislocation, thromboembolic disease, and other less common adverse effects.

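### Adverse events reach the CRF only if they relate to the device or operation, so relatedness filters events before capture, probably by staff who know the head type

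*Combined protocol and SAP*

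**What the plan says.** Section 4 sets the recording rule: "A record of all adverse events relating to subjected device (see Risk Analysis Section) and operative procedure" is to be entered on the CRF, "including details of the nature, onset, duration, severity, will be made on the" relevant CRF section. The details listed do not include causality or seriousness, and nobody is named as deciding whether an event relates to the device or operation. The next sentence is broader: "The subject will be questioned about any adverse event(s) at each subsequent follow-up assessment visit". No sentence says that an event reported in answer to that question, but thought unrelated, is recorded.

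Section 8, to which section 4 points, states: "Due to the investigational nature of the system, there are unknown risks".

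On knowledge of the arm, section 2.4.1 says "An operative record will be completed to record details of each operative procedure and of the used implants", and section 6.2 says "CRFs must be reviewed and signed by the Investigator or his/her designees". Neither section 2.5 (Randomization) nor any other section describes masking of surgeon, investigator, patient or assessor, or independent review of events.

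There is a second safety channel. Section 2.3 lists "Complications including revisions" as a secondary endpoint in both phases, and the schedule in section 2.4.2 has a row for it marked as applying at any time. Neither place limits it to related events, and neither defines a complication.

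**The concern.** Events are asked about widely and recorded narrowly, and the step between the two is a judgement. If that judgement is made by someone who knows whether the head is ceramic or cobalt-chrome, the threshold may differ between a new head and a familiar one. Equal true event rates could then look different, or a real difference could be hidden. Relatedness recorded as a field beside every event can be re-examined later. Used as an entry condition, it leaves nothing on the CRF to re-examine.

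The rule also sits awkwardly with the aim of the study. Section 1.1 says there are no clinical data on the Delta head against the E1 liner and that data on safety are needed. An effect nobody anticipated is the kind least likely to be judged related when it first appears.

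**Working it through.** The plan gives no event rate, no recording probability and no planned between-arm test of adverse events, so there is no figure to reproduce. The check is textual, followed by an illustration on assumed values.

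**Textual check**

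1. *Is there a filter?* Yes. Section 4 restricts the record to related events, and its question to patients is not so restricted.
2. *Who applies it?* Not stated. Site personnel complete the CRF and the investigator or a designee signs it (section 6.2). The site's operative record lists the implants (section 2.4.1). No masked assessor is described. That the assessor knows the head type is a strong inference, not a stated fact.
3. *Which events are exposed?* Those that depend on the adverse event record alone. Revisions and evident hip complications have the separate endpoint. Because a complication is undefined, that endpoint does not assure capture of unanticipated or systemic events.
4. *Can a filtered event be recovered?* Partly. Section 6.1 requires source records such as hospital or clinic notes, and section 6.2 lets the monitor compare originals with the CRF. But an unrelated event missing from the CRF complies with section 4, so that comparison has no reason to flag it.

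**Illustration (assumed values)**

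Inputs: 80 hips per arm (section 5.1), treated as independent, which is an approximation because bilateral patients receive the same head on both sides. The true risk *p* is assumed equal in the two arms. Fractions *r1* and *r2* of events are assumed to be recorded.

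Apparent ratio = (*p* × *r2*) / (*p* × *r1*) = *r2* / *r1*, whatever *p* is:

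- 90% v 70%: 0.70 / 0.90 = 0.78
- 80% v 50%: 0.50 / 0.80 = 0.63
- 90% v 50%: 0.50 / 0.90 = 0.56

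Expected recorded events = 80 × *p* × *r*. At *p* = 5% there are 80 × 0.05 = 4 true events per arm. Recorded counts are 4 × 0.90 = 3.6 v 4 × 0.70 = 2.8, or 4 × 0.80 = 3.2 v 4 × 0.50 = 2.0.

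Chance that a two-sided Fisher test at 5% declares a difference when none exists, by exact enumeration of two binomials with 80 hips each:

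| True risk | 90% v 90% | 90% v 70% | 90% v 50% |
|---|---|---|---|
| 5% | 1.4% | 1.7% | 2.9% |
| 10% | 2.7% | 4.1% | 9.7% |
| 20% | 3.1% | 7.2% | 23.8% |
| 30% | 3.3% | 10.7% | 39.6% |

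At 5% true risk with 80% v 50% recording the figure is 1.9%. For uncommon events, then, the harm is a distorted estimate and lost events, with almost no effect on test error. False significance becomes appreciable only for common events, or with a very large gap in recording.

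**The case against.** The best defence has four parts.

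- **The separate endpoint.** Complications including revisions are collected at any time with no stated relatedness limit. A reader might infer from section 4 that the trial records no safety event unless it is judged related. The documents do not support that: nothing says section 4 filters this endpoint. This part stands and narrows the point to the adverse event record.
- **The scope of section 8.** Its list of risks is expressly not exhaustive and covers most events in an operated hip. A reader might infer that the recording rule contradicts the admission of unknown risks. It does not, because the rule points to the very section that contains the admission. What remains is a tension: an unanticipated event still has to be judged related before it is recorded.
- **Source records.** It would be too strong to say that a filtered event leaves no trace or can never be reviewed. It may be in the clinic notes. It is absent from the data that would be compared by arm.
- **Unseen facts.** The assessor is not named, so it would be wrong to state as fact that unmasked investigators judge relatedness. The sample forms in Appendix 2 are not reproduced in the text available for this review and may be broader than section 4. All recording fractions above are assumptions, and wide gaps are hard to credit for objective events such as dislocation. Both limits stand, but section 4 is the stated rule, and a broader form would only show that the two need aligning.

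**Conclusion.** The point holds in a limited form. As written, section 4 makes relatedness a condition of entry to the adverse event record, with no masked or independent judge described. This could distort the between-arm comparison of adverse events, or leave unanticipated events off the CRF. Revisions and evident hip complications are less exposed.

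Neither the size nor the direction of any bias can be derived from the documents. The illustrated ratios of 0.56 to 0.78 rest wholly on assumed recording fractions and equal true risks, and at about 4 true events per arm the effect on test error is small. The conclusion also assumes that the forms follow section 4 and that site staff make the relatedness judgement. It is an inexpensive improvement to the safety data; it does not touch the wear endpoints or show that the safety results will be biased.

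**What to change.** In section 4, require the CRF to record every event in the operated hip and every serious adverse event, whatever the judged cause, with relatedness as a separate field. In the analysis section, state that all such events are reported by arm first and the related ones second.

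The cost is some extra CRF entries over 10 years. No new visit or question is needed, because patients are already asked about any event at follow-up. One limit remains: non-serious events outside the hip would still be recorded only if judged related, so an unanticipated mild systemic effect could still be missed. Defining a complication in the same edit would make clear which events the secondary endpoint captures independently of section 4.

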5. STATISTICAL ANALYSIS PLAN

5.1. Sample Size Calculation

The study population is calculated based on the primary endpoint of Poly wear at 10 year postop. A total of 160 hips will be recruited the study and randomly assigned to either CoCr or Ceramic head group. Each site is required to use the same stem and cup for both CoCr and Ceramic groups.

Significance Level = 5 % (95% confidence)

$d = 0.5$ mm Clinically significant difference in wear.

$\xi = 0.07$ Estimate standard deviation of wear.

$N = 63$

Take into consideration of Lost-to-Follow-up Rate = 20% for 10 year

Final N = 80 hips per group

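### The printed sample-size inputs (d = 0.5 mm, SD 0.07 without a unit, alpha 5%) do not give N = 63, and the plan does not show which figure is wrong

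*Combined protocol and SAP*

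**What the plan says.** Section 5.1 of the combined protocol and SAP names the basis for the trial's size: "The study population is calculated based on the primary endpoint of Poly wear at 10 year postop". It then lists:

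- alpha: "Significance Level = 5 % (95% confidence";
- the difference to detect: "d = 0.5$ mm Clinically significant difference in wear";
- the SD: 0.07, described as "Estimate standard deviation of wear", with no unit and no source;
- N = 63;
- attrition: "Take into consideration of Lost-to-Follow-up Rate = 20% for 10 year";
- the result: "Final N = 80 hips per group", which makes 160 hips in all.

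The section does not give power, sidedness, or the test or formula. Section 2.4.1 describes the radiographic measurement as a rate rather than an amount: "the penetration rate will be measured by Hip Analysis Suite".

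**The concern.** A target difference about seven times the SD should need only a handful of hips, yet the section arrives at 63. The inputs and the output cannot all be right.

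Section 5.1 is the only justification in the plan for enrolling 160 hips, each to be followed for 10 years. If the SD really is 0.07 mm, the trial is far larger than a 0.5 mm target needs. If the SD is nearer 1.0 mm, the trial is only just large enough. A reader of the final result could not tell whether a null finding excludes the difference that the plan calls clinically significant.

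**Working it through.** **Inputs.** From section 5.1: d = 0.5 mm, SD = 0.07, alpha = 0.05, N = 63, loss 20%. From section 2.5: equal allocation. Assumed because not stated: two-sided test and 80% power, with other values tried.

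**Step 1: the attrition step.** 63/(1 − 0.20) = 78.75, printed as 80 per group. This step is consistent and indicates that 63 is a per-group figure. The fault lies earlier.

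**Step 2: the plan's own N from its own inputs.** Standardised difference = 0.5/0.07 = 7.143. Normal formula:

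n per group = 2(z_α + z_power)² / 7.143²

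| Power | Sidedness | n per group |
|---|---|---|
| 80% | two-sided | 2(1.960 + 0.842)²/51.02 = 0.31 |
| 90% | two-sided | 0.41 |
| 99% | two-sided | 0.72 |
| 99.9% | two-sided | 1.00 |
| 80% | one-sided | 0.24 |

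By two-sample t-test (noncentral t), power is 92.1% with 2 per group and 99.998% with 3. With 63 per group the expected test statistic is 7.143 × √(63/2) = 40.1, so power is essentially 100%. A one-sample formula gives 1. A confidence-interval precision formula gives (1.96 × 0.07/0.5)² = 0.08. None comes near 63.

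**Step 3: what would give 63.** Each reading below is an assumption, at two-sided 5%.

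- (a) *Standardised difference of 0.5.* The normal formula at 80% power gives 2(2.802)²/0.25 = 62.8, so 63 per group. The t-test gives 63.8, so 64; t-test power at 63 is 79.5%. This means d = 0.035 mm if the SD is 0.07 mm, or an SD of 1.0 mm if d = 0.5 mm is right. At 90% power the t-test would need 86 per group.
- (b) *Standardised difference of 0.714.* This is 0.05 mm with SD 0.07, or 0.5 mm with SD 0.7 (0.07 mm/year multiplied by 10 years). At 80% power it needs 30.8 per group (normal) or 31.8 (t-test), a two-group total of 61.5 to 63.5. Then 63 would be close to a total, against the per-group wording of the attrition step. With 63 per group, t-test power would be 97.8%.
- (c) *SD of 0.22 mm.* This is 0.07 per year with independent yearly scatter, 0.07 × √10 = 0.221. The t-test needs 5 per group at 80% power. This reading does not recover 63; it shows how far the unit of the SD matters.

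**Step 4: what 63 per group can detect at 80% power.** Detectable difference = SD × 2.802 × √(2/63) = 0.499 × SD.

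| SD (mm) | Detectable difference (mm) |
|---|---|
| 0.07 | 0.035 |
| 0.22 | 0.11 |
| 0.7 | 0.35 |
| 1.0 | 0.50 |

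**The case against.** Five points can be made for the plan.

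- *Unstated design choices might explain the gap.* They do not. Dividing alpha by six, for the five interim analyses and the final one, raises the 80% figure only to 2(2.638 + 0.842)²/51.02 = 0.47 per group. Full correlation between the two hips of bilateral patients would at most double it, to about 1.
- *The two inputs may be in different units*, 0.07 being mm/year and 0.5 a 10-year total. This is possible, but adjacent lines describe both simply as wear, and neither conversion in Step 3 gives 63 per group at 80% power.
- *A digit may have been lost when the text was read from PDF.* This cannot be excluded, but the values are legible and nothing in the text shows it. Comparing with the source calculation would settle it.
- *No reading with d = 0.5 mm at 80% power shows a materially undersized trial.* This stands for the readings tried: the only one needing clearly more hips adds 90% power, which the plan does not state. What is shown is a hip count that cannot be verified, not an inadequate trial.
- *The detectable differences treat hips as independent*, while section 2.5 gives both hips of a bilateral patient the same device. This also stands. With positive within-patient correlation, the Step 4 figures are best cases. It does not affect the mismatch.

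**Conclusion.** The sample-size statement is wrong as written. The printed d and SD need 1 hip per group by the normal formula and 2 to 3 by t-test, against a printed 63. This holds at every usual power and for one- or two-sided tests, so it does not rest on the missing power. It rests only on reading d and the SD in the same unit, which is how the section presents them.

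Which figure is wrong cannot be decided from the documents. The closest match is a standardised difference of 0.5, but that depends on an assumed 80% power. Across the readings, the requirement at 80% power by t-test runs from 2 to 64 evaluable hips per group. The difference detectable with 63 varies about 14-fold, assuming independent hips.

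**What to change.** Check section 5.1 against the original calculation and correct it so that the figures reproduce. State:

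- the intended difference and its unit;
- the SD, its unit (mm at 10 years or mm/year) and its source;
- power, and one- or two-sided alpha;
- the test or formula;
- confirmation that 63 is evaluable hips per group, as the attrition step implies.

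Then give the wear difference that this number can detect with the confirmed inputs, and how it relates to the difference regarded as clinically important. The 0.035 mm figure is one scenario and should not be adopted without that check.

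The cost is a check of the original calculation and the rewording of one section. The enrolment target needs review only if the confirmed inputs require more than 63 evaluable hips per group, for example 86 with an SD of 1.0 mm and 90% power. Until then there is no basis for changing 80 per group in either direction.

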5.1. Data Analyses

5.1.1. INTERIM

An interim data analyses will be conducted when all patients reach 1, 2, 3, 5 and 7 yr post-op follow-up.

5.1.2. FINAL

A final data analysis will be conducted upon study's completion.

6. DATA COLLECTION, HANDLING AND RETENTION

6.1. SOURCE DOCUMENTATION REQUIREMENTS

Source documentation for this study will be maintained to document the treatment and study course of a subject and to substantiate the integrity of the trial data submitted for review to the regulatory agencies. Source documentation will include, but not be limited to, worksheets, hospital and/or clinic or office records documenting subject visits including study and other treatments or procedures, medical history and physical examination information, laboratory and special assessments results, pharmacy records, device accountability records, and medical consultations (as applicable).

6.2. CASE REPORT FORMS

Data for this clinical trial will be collected and documented on the subject Case Report Forms (CRFs) provided, which may be in paper form or in an electronic form. Authorized study site personnel will complete CRFs only. CRFs must be reviewed and signed by the Investigator or his/her designees.

Since there is a potential for errors, inaccuracies, and misinterpretation in transcribing data onto the CRFs, the following documents must be available at all times for inspection and comparison to the CRFs by the study monitor where appropriate:

- data query forms
- originals and photocopies/certified copies of all relevant records and reports
- copies of test results

Sample CRFs to be used with this clinical trial are provided in Appendix 2.

6.3. ELECTRONIC DATA ENTRY

All sites will be required to complete and submit case report forms on Biomet's online database, Joint Assist, in a timely manner. Forms will be monitored for completeness and accuracy by Biomet Japan.

Further, it is imperative that the investigator answers all questions on the case report forms. All data should be accurate, indelible and legible.

7. DATA REPORTING

7.1. INTERIM REPORT

An interim report will be provided after each follow-up period.

7.2. FINAL REPORT

Final report will be provided after 10 yr follow-up period.

8. RISK ANALYSIS

This clinical study is to collect data on the E1 liner and Delta Ceramic and CoCr femoral head hip system which is intended to help the participant gain mobility and decrease pain. Risks associated with this Hip system include general surgical and Hip arthroplasty risks. Due to the investigational nature of the system, there are unknown risks.

General Surgical Risks

As with any surgical procedure, there are risks involved with total joint replacement surgery. Potential adverse events include, but are not limited to: early or late infection perhaps necessitating device removal; component dislocation; damage to nerves and blood vessels; fracture of the bone or device; device loosening; allergic reactions to the metallic devices; phlebitis; long-term swelling; pulmonary embolization; and delayed wound healing. Other potential adverse effects include: prolonged illness; hematoma; wound dehiscence and/or drainage; the need for blood transfusions and/or further surgery; or permanent pain; deformity; and inconvenience. Risks associated with the anesthetic are those such as permanent brain damage, pneumonia, blood clots, and heart attack. Rarely some adverse events may be

fatal. These possible adverse events are not unique to the 1 liner and Delta Ceramic and CoCr femoral head hip system and, as stated above, may occur with any total joint replacement surgery.

As with any joint replacement post-operative activity, limitations may be imposed depending upon the participant's age, general health, baseline (pre-operative) activity level and baseline (pre-operative) condition of the Hip and other joints.

Potential Risks Associated with E1 liner and Delta Ceramic and CoCr femoral head hip system

As with all hip replacement systems, potential adverse effects include risk of infection, loosening of the components, breakage or bending of the components, or change in position of the components any of which can necessitate removal and/or revision surgery. There have been reports of sensitivity reactions to the components of Hip systems. Other potential adverse effects of Hip replacement surgery include neurovascular damage, dislocation, thromboembolic disease, and other less common adverse effects.

1. Material sensitivity reactions. Implantation of foreign material in tissues can result in histological reactions involving various sizes of macrophages and fibroblasts. The clinical significance of this effect is uncertain, as similar changes may occur as a precursor to or during the healing process. Particulate wear debris and discoloration from metallic and polyethylene components of joint implants may be present in adjacent tissue or fluid. It has been reported that wear debris may initiate a cellular response resulting in osteolysis, or osteolysis may be a result of loosening of the implant.
2. Early or late postoperative infection and allergic reaction.
3. Intraoperative bone perforation or fracture may occur, particularly in the presence of poor bone stock caused by osteoporosis, bone defects from previous surgery, bone resorption, or while inserting the device.
4. Loosening or migration of the implants can occur due to loss of fixation, trauma, malalignment, malposition, bone resorption or excessive, unusual and/or awkward movement and/ or activity.
5. Periarticular calcification or ossification, with or without impediment of joint mobility.
6. Inadequate range of motion due to improper selection or positioning of components.

7. Dislocation and subluxation due to inadequate fixation malalignment, malposition, excessive, unusual and/or awkward movement and/or activity, trauma, weight gain, or obesity. Muscle and fibrous tissue laxity can also contribute to these conditions.
8. Fatigue fracture of component can occur as a result of loss of fixation, strenuous activity, malalignment, trauma, non-union, or excessive weight.
9. Fretting and crevice corrosion can occur at interfaces between components.
10. Wear and/or deformation of articulating surfaces.
11. Valgus-varus deformity.
12. Patellar tendon rupture and ligamentous laxity.
13. Intraoperative or postoperative bone fracture and/or postoperative pain.

Minimization of Risk

It is believed that none of the previously mentioned adverse events will occur in significant numbers. This study protocol has reduced the potential risk to the participant through the following methods:

1. By defining a participant population that limits the exposure of the device to participants conforming to the proposed indications, exclusions, and age requirements
2. The surgical technique has been developed to help eliminate potential operative difficulties.

